5.13.1. Compliance and exceptions

All sponsor personnel, all staff at the research center, as well as third parties involved in tasks described in this CIP must adhere to the CIP. A deviation is any failure, intentional or not, to follow the requirements of this CIP, including laws, guidelines, and other regulations, as well as applicable amendments. Deviations that could affect or have affected patient safety or the scientific integrity of the clinical investigation are considered major. Otherwise, they are considered minor deviations.

Incorrect, spurious, or lost data from the CRD are not considered deviations per se and are managed according to the queries procedures described in the data management section of this CIP. However, the underlying reason could be a deviation.

Under emergency conditions, deviations from the CIP can be undertaken without prior notice from the sponsor and the ethics committee if they are carried out to protect the rights, safety, and well-being of human subjects.

5.13.2. Storage, reporting and analysis of deviations

Research centers must automatically inform the monitor of any deviation they are aware of. Additionally, adherence to the CIP is verified by the sponsor through monitoring visits. Each specific deviation from the center is recorded by the monitors in the deviation log and analyzed to determine the necessary corrective or preventive actions. Additional information about the type of deviation, actions taken, and outcomes may be collected in the monitoring visit reports. All information in the deviation logs is consolidated by the sponsor in the study's global deviation log.

Deviations by sponsor personnel or third parties must be immediately reported to the sponsor by anyone who detects them. They are recorded in the study's deviation log and evaluated to determine the need for corrective or preventive actions.

Deviations are reported in the interim and final reports of the clinical investigation.

The sponsor adheres to the specifications of the ethics committees and competent authorities and ensures that timelines and schedules are met.

5.13.3. Corrective and preventive actions and disqualification criteria

Corrective actions will be taken to repair or prevent any negative consequences caused by a deviation. Preventive actions will be taken to ensure that the same type of deviation does not occur again. Each deviation will be individually assessed by the sponsor for the necessity of an immediate response. Additionally, the sponsor will regularly evaluate the global deviation log to determine the need for a global preventive action.

All persons involved in the deviation will need to cooperate with the sponsor, identifying and implementing appropriate actions. The performance and implementation of these actions will be documented by the sponsor and filed in the central file and, in the case of specific deviations, in the investigator's file.

Disqualification of study personnel is the last measure within possible preventive actions. This implies that in the case of significant deviations that substantially affect the safety and well-being of the subjects, or that lead to a high probability of data disqualification and doubts about the study results, and there is a probability of recurrence, the responsible person or the investigating center will be excluded from the study.

6. MONITORING PLAN

The sponsor will hire the company P INVESTIGA to carry out the study. Both the sponsor and P INVESTIGA will be responsible for ensuring compliance with the protocol and norms through proper monitoring. It is the sponsor's obligation, supervised by P

INVESTIGA, to ensure that the devices are used under the immediate supervision of the investigator. Like the investigator, the physician is responsible for conducting the study according to the signed research contract, the study protocol, applicable laws (including local regulations and the Declaration of Helsinki), and any conditions imposed by the study review committees.

The entries in the electronic CRF will be reviewed, and the source data will be verified at the hospital by the monitors to ensure that the investigator and the research team conduct the clinical investigation as stipulated in the protocol, the Declaration of Helsinki, ISO 14155, and local laws to guarantee adequate protection of the rights, safety of the subjects, and the quality and integrity of the resulting data.

A monitor will periodically visit the hospital during the study. All participating centers will be monitored throughout the study duration, with the frequency of these visits adjusted as necessary to ensure adherence to the procedures described in the protocol, as well as to ensure the highest possible data quality. A detailed monitoring plan previously developed by P INVESTIGA will be followed. Periodic monitoring will ensure, among other things, that the hospitals remain adequate, the protocol is being followed, the ethics committees have been informed of protocol changes, the files and data collection are complete and available, the reports have been made and submitted on time to the sponsor and authorities, and that the investigator is fulfilling all their obligations.

Periodic monitoring will include, but not be limited to:

- 1. Completing and delivering the necessary electronic CRFs and other relevant study documentation
- 2. Continuous evaluation of the centers, including the storage and maintenance of the investigational devices
- 3. Adherence to the clinical investigation plan
- 4. Adherence to the current version of ISO 14155 and local regulations.

If the monitor becomes aware that the investigator is not meeting the requirements mentioned above, the monitor will be obliged to notify the sponsor and P INVESTIGA staff, who will review the situation and proceed to implement corrective plans, suspend recruitment, or, as a last resort, close the research center.

7. RESPONSABILITIES.

The ReDS-SAFE HF II study will be coordinated and controlled by the principal investigator:

[name] [name] Hospital Universitario Ramón y Cajal Department of Cardiology, Advanced Heart Failure Unit [name]

The principal investigator, as well as the members of the executive committee, will be responsible for the following processes as described in ISO14155:2011:

- Creation/review of the research plan
- Control of the study's performance and progress
- Continuous monitoring of the risk/benefit ratio
- If necessary, making the decision to prematurely terminate the study after consulting with the sponsor
- Coordination of the publication and presentation of study results
- Advising all investigators on medical issues related to the study
- Reporting adverse events

The clinical coordinators of the study will be assisted in all described tasks by the Study Coordinator/Project Manager. Additionally, they have the same rights and obligations as the rest of the investigators.

7.1. Responsibility of investigator

This study will be conducted by qualified investigators whose participation has been approved by the sponsor after careful analysis and documented in a clinical contract detailing the tasks. The principal investigator specified in the contract will be considered the principal investigator for that specific center. The principal investigator may delegate some of their functions to co-investigators. However, the principal investigator retains primary responsibility for the correct execution of the study in their center according to the following responsibilities (as defined in ISO14155:2011):

- Register the study with the responsible authorities at their center (hospital administration)
- Communication with the ethics committee and obtaining its dated and signed approval
- Reporting adverse events
- Active recruitment of candidate patients and providing appropriate medical care to patients participating in the study
- Patient education and obtaining written informed consent as described in the protocol
- Safe and effective use of study devices
- Conducting the study as described in the protocol
- Completing the CRFs within the corresponding time windows
- Confidential treatment of all study-related documents and information

If an investigator does not comply with the signed contract or the protocol and it is not possible to reach an agreement between the investigator and the sponsor, the sponsor is authorized to exclude the investigator from the study.

7.2. Responsibility of Steering Committee

It is formed by relevant members in the field of heart failure and the president of the patient association with cardiovascular disease Cardioalianza. This committee will be available for consultation on the main objectives, promotion, publication, and presentation of the study results. The scientific committee advises especially during the design phase of the research plan, and with the continuous control of safety in the execution of the study.

The members of this committee are:

[name]

[name] [name]

[name]

[name]

[name]

[name] [name]

[name]

7.3. Responsibility of Sponsor

The sponsor of this clinical study is Fundación para la Investigación Biosanitaria Ramón y Cajal Hospital Universitario Ramón y Cajal [name]

The sponsor ensures that all necessary documents, information, and human resources will be available at the start and during the study. Additionally, the sponsor will have the following tasks and obligations:

- Select appropriate research centers and investigators in accordance with the clinical coordinator.
- If necessary, report to all relevant authorities and provide reports according to national laws.

7.4. Responsibility of Clinical Coordinator

In case of any issues related to the clinical research plan and the medical devices used, the investigator should contact the clinical coordinator, who is responsible for the following:

- Assisting the Principal Investigator in the preparation of the protocol and its possible amendments.
- Assisting investigators during the study (securing the approval of research review committees/ethics committees and publication of study results, etc.),
- Providing regular information to the investigators about the progress of the study.
- Organizing the handling of inquiries.
- Handling data and analyzing it.

The sponsor appoints the person described below as the study coordinator:

[name] [name]

Hospital Universitario Ramón y Cajal

Cardiology Department, Advanced Heart Failure Unit

[name].

7.5. Responsibility of Clinical Events Committee

All events related to the primary objective and secondary objectives will be reviewed by the Clinical Events Committee. This committee will consist of three physicians not participating in the study who will review all events recorded by the patients. Their function will be to assign the type of adverse event according to its severity and relevance to the study.

The members of this committee will be [name], [name], and [name], from the Cardiology, Internal Medicine, and Nephrology departments of Hospital Universitario Ramón y Cajal.

[figure not shown]

Annex 3: ReDS guided diuretic protocol

ReDS (%)	Diuretic Protocol
Less than 20%	Discontinue diuretics.
20-35%	Maintain the prescribed diuretic dose. Consider switching from intravenous to oral administration if no significant edema is present. If significant edema persists, continue intravenous.
36-45%	Increase the diuretic dose. Switch to intravenous administration if given orally. Add a thiazide diuretic if the intravenous dose is equivalent to 200 mg.
Greater than 46%	Add a second diuretic. Administer all diuretics intravenously and aim for an hourly diuresis of at least 250 ml in the next 2 hours. If this is not achieved, double the prescribed dose.

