1. SUMMARY

Residual congestion in hospitalized heart failure (HF) patients at discharge is one of the main causes of early readmission. The ReDS (Remote Dielectric Sensing) system is a non-invasive, easy-to-use, and rapid technique that accurately measures the proportion of fluid in lung tissue using RADAR technology. A pilot clinical trial (3 centers, 100 patients) led by the Principal Investigator (PI) demonstrated that guiding decongestion using the ReDS system during hospitalization was associated with a significant reduction in the 30-day readmission rate compared to standard clinical practice, without associated safety events.

Our current objective is to confirm the efficacy and safety of a ReDS-guided decongestion strategy in hospitalized congestive HF patients. To achieve this, an independent, randomized, single-blind clinical trial has been designed, enrolling up to 1,014 congestive HF patients in 25 Spanish hospitals. Patients will be randomized to a decongestion strategy, hospital discharge, and early follow-up in HF units based on ReDS system values versus a strategy based on current clinical practice. All patients will be evaluated daily during hospitalization and in two post-discharge visits (at approximately 10 and 30 days) in HF units using the ReDS system. However, information will only be available to clinicians in the intervention group.

The primary efficacy endpoint will be all-cause mortality, HF readmission, or HF-related decompensations at 30 days. The primary safety endpoint will be the rate of symptomatic hypotension, electrolyte imbalances, or worsening renal function at 30 days.

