5. METHODOLOGY

5.1. Study design (annex 1)

A randomized, single-blind, controlled, multicenter clinical trial (list of investigators and participating centers in annex 2) promoted by the researcher, which evaluates the efficacy and safety of a decongestion strategy guided by the ReDS system compared to standard clinical practice in patients admitted for decompensated heart failure.

5.2. Study population

Those adult patients meeting all the following criteria will be included:

- 1. Hospitalized due to HF as the main reason, including the presence of symptoms and signs of congestion, regardless of the left ventricular ejection fraction (LVEF).
- 2. NT-proBNP greater than 1000 pg/L or BNP greater than 300 pg/L upon admission.

Patients meeting any of the following conditions will be excluded:

- 1. Height less than 150 cm or greater than 190 cm or body mass index (BMI) less than 22 or greater than 39, conditions where the use of ReDS is not approved.
- 2. Patients requiring inotropes or vasopressors upon admission, with mechanical support, or heart transplant recipients.
- 3. Any malformation or variant affecting the right lung anatomy (e.g., a pacemaker).
- 4. Patients with any heart disease requiring a planned surgical intervention during the clinical trial (coronary disease, valve disease, or other).
- 5. Chronic kidney disease on hemodialysis.
- 6. Life expectancy less than 12 months due to non-cardiological origin.
- 7. Participation in another clinical trial with intervention.

5.3. Variables

- 1. Primary efficacy variable: combined 30-day outcome of all-cause mortality, heart failure (HF) readmission, or HF-related visits requiring diuretic treatment adjustment.
- 2. Secondary efficacy variable: individual components of the main variable, proportional change in natriuretic peptides and CA125 between admission and the first post-discharge outpatient visit, New York Heart Association functional class at the first post-discharge outpatient visit, average length of stay, cost of hospitalization for HF, and unplanned visit.
- 3. Primary safety variable: combined outcome of symptomatic systolic hypotension (<90 mmHg), electrolyte imbalances (potassium below 3 or above 5.5 meq/L), and/or worsening of renal function compared to the baseline visit at the first post-discharge outpatient visit (at least 50% reduction in glomerular filtration rate).

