5.4. Protocol

Patients will be identified and selected upon admission. If they meet the selection criteria and confirm their willingness to participate in the study, they will be randomized in a 1:1 sequence through a mobile application specifically designed for the study by P INVESTIGA, to one of the following interventions within 48 hours of hospital arrival:

1) "ReDS-guided strategy." Each day, the clinician responsible for the patient will have access to the ReDS value and will adjust the treatment according to the study's diuretic protocol (annex 3). The responsible physician can discharge the patient if the clinical stability criteria are met, and the ReDS value is below 35% and/or a reduction of 15% or more from the admission ReDS value has been achieved. If the ReDS criteria are not met, the patient must remain hospitalized for another day until these conditions are met. Clinical stability is defined as the presence of at least 2 of the following 3 conditions: i) discharge weight lower than admission weight, ii) at least a 20% reduction in natriuretic peptide from admission, and iii) a score <2 in the Orthoedema score.

2) "Usual clinical practice strategy." The responsible physician will not have access to the ReDS values and will adjust the treatment according to their clinical judgment and local practices. Discharge can be given if the clinical stability criteria are met.

The ReDS technology has been described in detail previously (7, 8, 20). Briefly, the ReDS system consists of 2 sensors that are placed (sitting or supine) on the front (infraclavicular) and back (below the scapula) of the patient's right hemithorax and in 45 seconds accurately quantifies the proportion of fluid in the lung. The sensors are connected via 1 cable to a touchscreen monitor that easily guides the measurement process and stores this information. The accuracy of this technology has been validated with high-resolution chest computed tomography (8) and invasive hemodynamic measurements with a Swan-Ganz catheter (9). Normal ReDS values range between 20% and 35% (i.e., 20-35% of the lung would be fluid). Above 35% is considered congestive, whereas below 20% the lung would be "dry" or dehydrated.

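### The primary endpoint does not exclude planned clinic visits, so a diuretic change prompted only by a ReDS reading can count as a primary event, and only in the ReDS arm

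*Protocol*

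**What the plan says.** **Endpoint.** Protocol 5.3 item 1 defines the primary efficacy variable as a 30-day composite of death from any cause, HF readmission, or "HF-related visits requiring diuretic treatment adjustment". Objective 1.1 has the same third component. Neither excludes planned visits, gives the direction of the adjustment, or asks for worsening HF. Item 2 of 5.3 lists unplanned visits separately, among the secondary variables: "cost of hospitalization for HF, and unplanned visit".

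**Intervention after discharge.** The Summary says the randomised strategy includes "early follow-up in HF units based on ReDS system values". Sections 5.5.4 and 5.5.5 schedule a ReDS measurement in all patients at the clinic visits on day 14 ± 3 and day 30 ± 5 after discharge. Of these readings the Summary says "information will only be available to clinicians in the intervention group".

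**What a high reading means.** Section 5.4 states "Above 35% is considered congestive". During admission the ReDS-arm clinician "will adjust the treatment according to the study's diuretic protocol (annex 3"), and the Annex 3 row for 36-45% reads "Increase the diuretic dose. Switch to intravenous administration if given orally".

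**Discharge.** A clinically stable ReDS-arm patient can be discharged if "the ReDS value is below 35% and/or a reduction of 15% or more from the admission ReDS value has been achieved". The fall alone is enough, so discharge above 35% is allowed.

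**Event review.** Section 5.9 has a committee blinded to study group review reported events. Neither 5.9 nor 7.5 tells it how to treat a diuretic change made because of a ReDS value.

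**The concern.** One arm's clinicians see a number at a scheduled visit, are expected to act on it, and the natural action is a diuretic change. The primary endpoint counts HF-related visits at which diuretics are adjusted. A step of the randomised strategy can therefore be scored as its failure.

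A control patient with the same lung fluid at the same visit has no reading-driven route to an event, because the clinician does not see the value. Control patients can still have changes made on symptoms, examination or biomarkers, so the asymmetry concerns reading-driven changes only.

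The ReDS-arm event rate would be inflated, the estimated effect pulled towards no difference, and power reduced. Centres that do and do not report such changes as events would also give different primary results from the same patients. Blinded review does not by itself correct this: a committee that knows neither the arm nor the reason for the change cannot tell a reading-driven change from a clinical one without a rule.

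**Working it through.** **1. Can a planned visit produce a primary event?** The start of the 30-day window is not stated; I assume it runs from discharge.
- First clinic visit: days 11-17, always inside the window.
- Final clinic visit: days 25-35, inside only if held by day 30.
- The definition requires an HF-related visit and a diuretic adjustment. A scheduled HF-clinic visit at which the dose is changed fits that wording.

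**2. Who is exposed?** Any ReDS-arm patient with a reading above 35% at a clinic visit. One such group follows from the discharge rule, reading the 15% fall as relative to the admission value:
- Admission 45%: 45 × 0.85 = 38.25% at discharge.
- Admission 50%: 50 × 0.85 = 42.5%.
- A discharge reading of 36% or more is allowed from an admission value of 36 / 0.85 = 42.4%.
- If the 15% means percentage points, the threshold is 36 + 15 = 51%.

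A patient discharged at 38.25% and unchanged two weeks later still has a reading that 5.4 calls congestive.

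**3. The plan's own figure.** Section 5.6 gives a 15% control rate, a 50% reduction (so 7.5%), 80% power, 5% alpha (taken as two-sided), 10% loss and 507 per group. The two-proportion formula is

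n = [1.96 √(2p̄(1−p̄)) + 0.84 √(p₁(1−p₁) + p₂(1−p₂))]² / (p₁−p₂)², with p̄ = 0.1125.

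It gives 278 per group, and 278 / 0.9 = 309 after loss. The stated 507 is not reproduced. With 507 × 0.9 = 456 evaluable per arm,

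power = Φ{[0.075 √456 − 1.96 √(2 × 0.1125 × 0.8875)] / √(0.1275 + 0.0694)} = Φ(1.64) = 95%.

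The starting power below is therefore 95%, not the stated 80%.

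**4. Sensitivity to reading-driven events.** Let q be the share of otherwise event-free ReDS patients who gain an event only through a reading-driven change. The protocol gives no value, so q is an assumption. The ReDS-arm rate becomes 0.075 + 0.925q, the control rate stays at 15%, and 0.925 × 456 = 422 patients are at risk of reclassification.

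| q | Added events | ReDS-arm rate | Risk ratio | Power, 456 per arm |
|---|---|---|---|---|
| 0 | 0 | 7.5% | 0.50 | 95% |
| 1% | 4 | 8.4% | 0.56 | 87% |
| 2% | 8 | 9.4% | 0.62 | 74% |
| 3% | 13 | 10.3% | 0.69 | 57% |
| 5% | 21 | 12.1% | 0.81 | 24% |

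Power reaches 80% at q = 1.6%, about 7 patients. The two rates are equal when 0.925q = 0.075, so q = 8.1%, or 34 of 422 patients.

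If true power were only the stated 80% (278 evaluable per arm), the same formula gives 53% at q = 2%.

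**The case against.** **Narrower intent.** The Summary describes this component as HF decompensation, and 5.3 speaks of visits that require an adjustment. A stable patient with an unchanged reading is not obviously decompensated, and the events committee might decline such a case. This stands as evidence of intent, but the operative definitions in 5.3 and objective 1.1 do not carry it. Detailed adjudication rules may sit in a charter or SAP that is not shown, so the lack of one here is not a separate fault.

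**Annex 3 in clinic.** A reader might infer that Annex 3 orders escalation at the clinic visits. The protocol does not say so. Section 5.4 ties the table to daily inpatient care, and its rows read as ward instructions. The point does not need the table: follow-up based on ReDS, with values above 35% called congestive, is enough for a clinician to act on the reading.

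**Discharge rule against Annex 3.** A reader might also infer a contradiction, because discharge at 36% or more can coincide with a row that calls for intravenous escalation. The conflict is softer than it looks. Discharge is permitted, not required, and needs clinical stability; a clinician can satisfy both texts by treating and keeping the patient. The endpoint bias does not depend on it.

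**Control-arm changes.** Control clinicians have examination, natriuretic peptides, CA125 and any locally used ultrasound at the same visits, and changes based on these count too. This is true, and it means that the net difference between arms cannot be predicted from the text. It does not create a reading-driven route to an event in the control arm.

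**Size.** No document gives q. This stands in full.

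**Conclusion.** The point holds as a defect in the primary endpoint definition. As written, a diuretic change that is part of the ReDS strategy can count as a primary event at a planned visit, and the reading that prompts it is visible in one arm only. This mechanism biases the comparison against ReDS.

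Its size is unknown. The power figures show that the design is sensitive to a few reclassified patients; they do not forecast a loss. They assume a 30-day window from discharge, a two-sided 5% test of proportions, 456 evaluable per arm, true rates of 15% and 7.5%, and an invented range for q. The 95% starting point depends on 507 per group being more than the stated inputs require.

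The documents do not support the stronger statements that Annex 3 compels these changes in clinic, that the discharge rule causes the bias, or that only the ReDS arm can have diuretic-adjustment events at planned visits.

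**What to change.** In 5.3 item 1 and objective 1.1, limit the third component in both arms to *unplanned HF visits requiring diuretic intensification for worsening HF*. This brings both in line with the Summary's description.

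Then:
- report diuretic changes at the two planned visits by arm, as a process measure and not as primary events;
- add a sensitivity analysis that also counts planned-visit intensifications supported by documented worsening symptoms or signs, adjudicated without the ReDS value.

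ReDS thresholds, Annex 3 and the discharge rule stay as they are.

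**Cost.** Redefining the primary endpoint is a substantial amendment under 5.13 and needs ethics committee approval and notice to centres. It adds no patients or procedures. Some genuine decompensations found at planned visits leave the primary endpoint in both arms; the sensitivity analysis is there to show whether that matters.

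The control rate may fall below 15% if the 2023 figure included planned-visit changes, which the protocol does not say. With a 50% reduction and 456 per arm, the same power formula gives 89% for 12% vs 6% and 82% for 10% vs 5%, so the planned sample size leaves room for the change.

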If changes to the clinical investigation plan (CIP) are necessary during the study, a justification for the change must be prepared, including the reason for the change. The modification of the CIP can be summarized in a separate document as an appendix to the current version of the CIP or result in a new version of the CIP. If the changes impact procedures related to the study or data analysis, they are defined as substantial. New versions of the CIP or substantial amendments must be reviewed and confirmed by the Coordinating Investigator. All investigators must acknowledge receipt of the amendment through the signature of the approval form for the amendment. Before implementing any changes, substantial amendments must be approved by the ethics committee and, if applicable, by the competent authorities. Non-substantial amendments will only be submitted for notification.

The investigator must not implement any deviation from the CIP without the sponsor's approval and without prior review and documented approval from the EC (and competent authorities if necessary). The only exception would be the need to eliminate an immediate risk to patients or if the change involves logistical and administrative aspects of the study.

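### Annex 3 binds the ReDS-arm clinician to escalate diuretics on the ReDS value, with no blood pressure, potassium, renal or clinical-judgment condition, so a non-emergency safety hold is a protocol deviation

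*Protocol*

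**What the plan says.** In the ReDS arm, section 5.4 says that each day the responsible clinician "will have access to the ReDS value and will adjust the treatment according to the" study's diuretic table, Annex 3. For the control arm, the same section leaves treatment to the physician's judgment and local practice.

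Annex 3 has four rows:
- **Below 20%:** stop diuretics.
- **20-35%:** keep the dose, with a modifier for edema: "Consider switching from intravenous to oral administration if no significant edema is present".
- **36-45%:** "Increase the diuretic dose. Switch to intravenous administration if given orally", with a thiazide added once the intravenous dose reaches the equivalent of 200 mg.
- **Above 46%:** add a second diuretic and use the intravenous route for all of them, with this target: "aim for an hourly diuresis of at least 250 ml in the next 2 hours. If this is not achieved, double the prescribed dose".

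On departures from the protocol, section 5.13.1 requires everyone at the center to adhere and states: "A deviation is any failure, intentional or not, to follow the requirements of this CIP". Section 5.13 says that the investigator may not deviate without the sponsor's "approval and without prior review and documented approval from the EC" (and the authorities where needed). It continues: "The only exception would be the need to eliminate an immediate risk to patients", or a logistical or administrative change. Section 5.13.1 separately allows deviations without prior notice in an emergency, to protect participants.

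**The concern.** Hypothesis 2.3 is that the ReDS strategy is as safe as standard care for symptomatic hypotension, electrolyte disturbance and worsening renal function. Followed literally, Annex 3 adds diuretic in a patient who is already developing one of these, provided the ReDS reading is high enough. A clinician who sees a drifting pressure, a falling potassium or a rising creatinine, none of them yet an emergency, finds nothing in the protocol that permits a hold. The choice is to escalate against judgment or to depart from the protocol. What is at stake is mainly patient safety at the bedside. A lesser matter is that reasonable safety holds are classed as deviations, and only in the ReDS arm, because the control arm has no dosing table to depart from.

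**Working it through.** The protocol states no figure on this point, so the check sets its provisions side by side.

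**1. Is Annex 3 binding?** Yes. The wording of 5.4 is mandatory. Judgment is granted in writing to one arm, so it cannot simply be read into the other.

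**2. Do the escalation rows carry a safety condition?**

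| Annex 3 row | Order | Condition beyond the ReDS value | BP, potassium, renal or judgment condition |
|---|---|---|---|
| <20% | Stop | None | Not an escalation |
| 20-35% | Maintain | Edema (route) | Not an escalation |
| 36-45% | Increase, intravenous, thiazide | Current route and dose | None |
| >46% | Second diuretic, intravenous, possible doubling | Urine output | None |

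Two of four rows escalate, and 0 of those 2 carry a safety condition. The urine target in the last row is 250 ml/h x 2 h = 500 ml. Missing it leads only to a doubled dose, whatever the reason for the low output. Blood pressure, potassium and filtration rate appear in 5.3 as outcome definitions, not as reasons to hold treatment.

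**3. Are susceptible patients enrolled?** Section 5.2 excludes patients on hemodialysis, on mechanical support, or needing inotropes or vasopressors upon admission. It does not exclude low pressure, low potassium or renal disease short of hemodialysis. Objective 2.1 names chronic renal insufficiency and diuretic resistance as subgroups of interest. A missed urine target is plausible in both.

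**4. What is the status of a hold?** By the definition in 5.13.1 it is a deviation. An immediate risk (5.13) or an emergency (5.13.1) permits it. Those exceptions do not clearly reach a same-day hold for a non-emergency trend. The prior-approval sentence in 5.13 is addressed to the investigator, and 5.9 says that researchers are separate from the treating team. Whether the sentence reaches the treating clinician is therefore not settled.

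**5. Can the order repeat from day to day?** The ReDS part of the discharge rule in 5.4 is met if "the ReDS value is below 35% and/or a reduction of 15% or more from the admission ReDS value has been achieved". Read the 15% as a relative reduction:
- A reading of 36% meets it when 36 <= 0.85 x admission value, that is, when the admission value is at least 36 / 0.85 = 42.35%.
- Admitted at 40%: 0.85 x 40 = 34.0%. Readings of 36% or more fail the criterion and also call for escalation (leaving aside 46% itself, which is in neither row).
- Admitted at 50%: 0.85 x 50 = 42.5%. The criterion can be met while the reading is still in the 36-45% row.

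If 15% means percentage points, the cut-off is 36 + 15 = 51%. Repeated escalation is thus built in for lower admission values and not for higher ones. The protocol does not give the distribution of admission values.

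**The case against.** The strongest reply is that a value-driven algorithm is the intervention under test, and that overrides dilute it. There is also real mitigation. The 36-45% row fixes no increment, so a very small increase complies. Nothing in Annex 3 prevents potassium replacement. Diuretics stop below 20% and are not raised at 20-35%. The entry criteria remove some of the highest-risk patients, overt emergencies are covered, and section 7.1 makes appropriate care an investigator duty. Section 5.8 reports no significant safety differences in the preceding randomized trial.

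Much of this stands and limits the size of the point. It does not close the gap. Latitude over the size of an increase is not permission to withhold it. Section 7.1 does not say that Annex 3 yields to clinical care, and the same list requires the study to be run as the protocol describes. The preceding trial had 100 patients, and section 2 itself advises caution because of its size. The interim looks at 30% and 60% and the committees act at trial level, not on a given day's dose.

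Three stronger readings are tempting, and the document does not support them:
- **Every non-emergency hold needs prior sponsor and ethics committee approval.** A reader might infer this from 5.13 and 5.13.1 together. The approval sentence names the investigator, 5.9 separates researchers from treating clinicians, and 5.13.1 makes a hold a deviation without extending the approval rule to all staff.
- **Adherence to the algorithm becomes unreadable.** Section 5.13.1 grades deviations as major or minor, and 5.13.2 has each one recorded and analyzed, with room to note its type. The log could separate safety holds from other non-adherence.
- **The primary or safety comparison is biased.** Section 5.6 specifies intention to treat, and nothing here shows a bias in either analysis.

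**Conclusion.** The point holds as a limited gap in patient safety and drafting. A binding dosing table orders more diuretic in two of its four rows with no safety or judgment condition, and a non-emergency hold is a deviation by the protocol's own definition. The protocol does not settle whether prior approval is also needed, and that uncertainty is itself worth removing.

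The size cannot be put as a rate. The protocol does not say how often a reading of 36% or more coincides with low pressure, low potassium or worsening renal function. The conclusion assumes that the mandatory wording in 5.4 is meant literally and that no hold rule exists outside the text available. Dosing and deviation rules belong in the protocol, so this is not a matter left to a statistical analysis plan. It is a cheap improvement worth making and does not threaten the trial's main conclusion.

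**What to change.** **Annex 3 and section 5.4.** Add that the responsible clinician may withhold or reduce any escalation step, including the dose doubling above 46%, when in their documented judgment one of these makes it unsafe: low or falling blood pressure, low or falling potassium, or worsening renal function on the latest local result. Give systolic pressure below 90 mmHg and potassium below 3 meq/L as explicit hold triggers, using limits already in 5.3. Say that they are not the only triggers, because those two cut-offs alone would miss much of the non-emergency range.

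**Section 5.13.1.** State that such a documented override is permitted by the protocol and is not a deviation. This also settles the approval question.

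**Data and reporting.** Record each override and its reason in the eCRF, and report the counts in the interim and final reports, since they would no longer enter the deviation log.

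**Cost.** Two short clauses, one eCRF field and one reporting line. Adherence to the ReDS algorithm becomes slightly looser. Blood pressure is already recorded daily (5.5.2), but the daily visits list no blood tests. The potassium and renal triggers would therefore rest on local testing and may be used unevenly across centers.
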